The likelihood ratio of a positive and a negative result for ultrasonography were 10.74 and 0.03 respectively, and that for capnography were infinity and 0.04 respectively.

The kappa value was 0.749 (95% CI: 0.567 – 0.931) which meant a good degree of agreement of result between these two methods.

The average time taken for confirmation of endotracheal tube by ultrasonography and capnography were 26.79 ± 7.64 seconds and 43.03 ± 8.71 seconds (mean \pm standard deviation) respectively. The median time for confirmation was 26 seconds with interquartile range [15 - 37] seconds for ultrasonography and 42 seconds with interquartile range [29 - 55] seconds for capnography. Ultrasonography was found to be faster than capnography by 16.36 ± 3.23 seconds (mean \pm standard deviation) and the difference in time was significant ($p = 0.011$).

Conclusion:

Ultrasonography and waveform capnography are both reliable and accurate methods of confirming endotracheal tube position. The use of ultrasound with capnography will help reduce time and increase precision of confirming endotracheal tube position. Ultrasound can confirm endotracheal tube position before manual bag ventilations, and thus may prevent aspiration of gastric contents into patient's lungs.

Keywords: Endotracheal intubation; ultrasonography; capnography.

TABLE OF CONTENTS

Serial No.	Contents	Page No.
1	Introduction	7
2	Literature Review	19
3	Objectives	30
4	Hypothesis	31
5	Methodology	32
6	Results	45
7	Discussion	55
8	Limitations	68
9	Conclusion	69
10	Recommendations	70
11	References	71
12	Appendices	
	Appendix A - PAC Form	77
	Appendix B - Consent	79
	Appendix B – Proforma	80
	Appendix D – Thesis approval letter from IRB	82

LIST OF ABBREVIATIONS

%	Percentage
>	Greater than
<	Lesser than
±	Plus– Minus
α	Alpha
ACLS	Advanced Cardiac Life Support
AHA	American Heart Association
ASA	American Society of Anesthesiologists
β	Beta
BMI	Body Mass Index
BPM	Beats Per Minute
CI	Confidence Interval
CL	Cormack Lange
CO ₂	Carbon Dioxide
COPD	Chronic Obstructive Pulmonary Disease
CPR	Cardiopulmonary Resuscitation
DLT	Double-Lumen Tube
ECG	Electrocardiogram
Eg	Example
ET	Endotracheal
ETCO ₂	End Tidal CO ₂
NIBP	Non-Invasive Blood Pressure
IRB	Institutional Review Board

IOM	Institute of Medicine
IQR	Interquartile Range
κ	Kappa value
Kg	kilogram
LMA	Laryngeal Mask Airway
LR ⁺	Likelihood ratio of a positive test
LR ⁻	Likelihood ratio of a negative test
MCVTC	Manmohan Cardiothoracic Vascular and Transplant Center

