Both capnography and ultrasound are safe and have been shown to be reliable methods of endotracheal tube confirmation in previous studies which will be detailed further in literature review section. Physicians with basic knowledge about these methods can use them in operating rooms and also in emergency rooms and wards. Ultrasound machines are now gaining popularity and their access extends from operation theatres, emergency rooms and even many primary health centres in Nepal.

Conducting this study will help us to see if ultrasound when used along with capnography can reduce time taken and increase precision for endotracheal tube confirmation inside operating theatres; and further advocate use of ultrasound imaging prior to manual ventilation for endotracheal tube confirmation in full stomach or patients at risk of aspiration.

LITERATURE REVIEW

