After confirmation of the endotracheal tube position, true and false positives and negatives were determined for both the methods as depicted in table 1.

Sensitivity, specificity, positive predictive value and negative predictive value, likelihood ratios; for both ultrasonography and capnography were calculated using their corresponding formulas.³⁷ The results were extrapolated into confidence intervals using Clopper-Pearson confidence interval.³⁷

Table 1. Designation of true and false positives and negatives.

Capnography		Ultrasonography	
Tracheal outcome	Oesophageal outcome	Tracheal outcome	Oesophageal outcome
True positive (TP): final position in trachea.	True negative (TN): final position in oesophagus.	True positive (TP): final position in trachea.	True negative (TN): final position in oesophagus.
False positive (FP): final position in oesophagus.	False negative (FN): final position in trachea.	False positive (FP): final position in oesophagus.	False negative (FN): final position in trachea.

Sensitivity = TP / (TP+FN).

Specificity = TN / (TN+FP).

Positive predictive value (PPV) = TP / (TP+FP).

Negative predictive value (NPV) = TN / (TN+FN).

Confidence intervals, CI (at 95 % level of confidence): for example for sensitivity

CI = (Sensitivity + 1.96SE, sensitivity – 1.96SE). Where SE is standard error,

SE for sensitivity = square root of [sensitivity (1 – sensitivity)/(TP+FN)]³⁷

Accuracy = $(TP+TN) / (TP+TN+FP+FN)$.

(TP=True Positive, TN=True Negative, FP=False Positive, FN= False Negative)

Likelihood ratio of a positive test: was given by

$$LR_{+} = \frac{\text{sensitivity}}{1 - \text{specificity}}$$

The positive likelihood ratio values corresponded to different probabilities as follows³⁷:

Table 2. Interpretation of positive likelihood ratio.³⁷

Positive likelihood ratio value	Probability
0	Excluded disease.
> 10	Large change in likelihood (or in other words high probability of any individual having a positive result on using the diagnostic test).
5 – 10	Moderate change in likelihood.
2 – 5	Small change in likelihood.
1	No change.

Likelihood ratio of negative test: was given by

$$LR_{-} = \frac{1 - \text{sensitivity}}{\text{specificity}}$$

The negative likelihood ratio values also corresponded to different probabilities as follows³⁷:

Table 3. Interpretation of negative likelihood ratio.³⁷

Negative likelihood ratio value	Probability
infinity	Excluded normality.

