Both ultrasonography and waveform capnography were found to be good, reliable and fairly accurate diagnostic methods of confirming endotracheal tube position. Ultrasonography was comparable diagnostically with capnography for endotracheal tube confirmation. The comparisons of the pretest and posttest probabilities of the two methods are shown in table 10.

Table 10. Comparison of the diagnostic characteristics of ultrasonography and waveform capnography.

	Ultrasonography	Waveform Capnography
Sensitivity in % (95% CI)	97.62 (91.66- 99.71)	96.43 (89.92 - 99.26)
Specificity in % (95% CI)	90.91 (58.72 - 99.77)	100 (71.51 - 100)
PPV in % (95% CI)	98.80 (92.67- 99.81)	100 (100 – 100)
NPV in % (95% CI)	83.33 (55.66 - 95.22)	78.57 (54.69 - 91.76)
Accuracy in % (95% CI)	96.84 (92.92 - 100)	96.84 (92.92 - 100)
Positive likelihood ratio	10.74	Infinity
Negative likelihood ratio	0.03	0.04

(CI= Confidence Interval, PPV= Positive Predictive Value, NPV= Negative Predictive Value)

Both ultrasonography and capnography together had correctly identified 10 out of the 11 oesophageal intubations. The 84 tracheal intubations were correctly identified by both ultrasonography and capnography or either one of these methods. Using the same formula (page 35), the combined accuracy of both the methods together was 98.94% (94 divided by 95, in percentage).

The analysis of agreement between the ultrasonography and capnography results was done using Cohen's kappa statistics. A kappa value of 0.749 with 95% confidence interval of (0.567 – 0.931) and standard error of 0.093 was found. The kappa value therefore showed a good agreement between the result of these two methods.

Time taken for endotracheal tube confirmation

Real-time ultrasonography was faster than waveform capnography for endotracheal tube confirmation in all cases. The mean time for confirmation by ultrasonography was 26.79 ± 7.64 seconds (mean \pm standard deviation). The mean time for confirmation by capnography was 43.03 ± 8.71 seconds.

The mean difference in time was 16.36 seconds (95% CI: 15.70sec – 17.02 sec). The median difference in time was 16 seconds. The standard deviation in difference in time was 3.23 seconds. The standard error of mean (SEM) was 0.332 seconds. The difference in time was highly significant ($p = 0.011$).

Table 11. Time taken for endotracheal tube confirmation.

	Range (in seconds)	Mean \pm SD (in seconds)	Median (in seconds)	IQR (in seconds)	p-value

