This study used both sidestream and mainstream capnographs. This was because of availability of different types of capnograph at the study sites. The details of sampling line delay are discussed later.

Ultrasonography vs Capnography

Both ultrasonography and waveform capnography were found to be good, reliable and fairly accurate diagnostic methods of confirming endotracheal tube position. Though ultrasonography and capnography were equally sensitive and capnography seemed more specific; the sensitivity, specificity, PPV, NPV of ultrasonography were comparable (statistically not different as seen by their confidence intervals) to waveform capnography.

The combination of ultrasonography and capnography increased precision (accuracy) over using either one of them in this study. Since the studies done previously had compared ultrasonography against capnography as the standard and thus calculated the sensitivity, specificity, PPV, NPV of ultrasound; these were not able to show if ultrasound had increased accuracy over using capnography alone.

Both of these methods are now known to be equally reliable. Hence in case of unmatched result given by these two methods in a patient, a third highly reliable method of confirmation has to be used because both ultrasonography and capnography have statistically not different false positive (1 – specificity) and false negative (1 – sensitivity) rates.

There was generally good agreement between the results produced by ultrasonography and capnography as shown by the kappa value of 0.749 with 95% confidence interval of (0.567 – 0.931). Other studies have shown a good or a very good agreement of these two methods by kappa statistics. The kappa value calculated by Adi et al³⁰, Chou et al²⁸, Karacebay et al²⁷ and Chintamani et al³⁴ were 0.85, 0.93 (0.84 – 1.00), 0.85 and 0.76 respectively.

Real-time, transtracheal, transverse suprasternal ultrasonography was significantly faster ($p = 0.011$) than capnography by 16.36 ± 3.23 seconds (mean \pm SD) in confirming endotracheal tube position in this study. The subgroup analysis between mainstream and sidestream capnographs also showed that the type of waveform capnograph device used did not affect the significant difference in time of ultrasound over capnograph in confirming endotracheal tube position.

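### The combined accuracy of 94/95 rests on a combination rule the Methods do not define, and the paired data show neither a gain from combining the tests nor that the two are equal

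*Combined protocol and SAP*

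**What the plan says.** The Methodology defines sensitivity, specificity, predictive values and accuracy for each test on its own: "true and false positives and negatives were determined for both the methods as depicted in table 1". Neither that section nor Statistical Analysis says how two results are to be merged into one. The only planned comparison of the two tests' results is kappa.

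The combined figure first appears in the Results, after Table 10. The text there says "Both ultrasonography and capnography together had correctly identified 10 out of the 11 oesophageal intubations" and "The 84 tracheal intubations were correctly identified by both ultrasonography and capnography or either one of these methods". Citing the single-test accuracy formula, it then concludes that "the combined accuracy of both the methods together was 98.94% (94 divided by 95, in percentage". No sensitivity, specificity or confidence interval is given for the combination.

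The Rationale names this gain as a purpose of the study: to see whether ultrasound used with capnography "can reduce time taken and increase precision for endotracheal tube confirmation inside operating theatres". The Abstract concludes: "The use of ultrasound with capnography will help reduce time and increase precision of confirming endotracheal tube position". The Discussion states: "The combination of ultrasonography and capnography increased precision (accuracy) over using either one of them in this study". The Conclusion repeats the point.

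The Discussion (Ultrasonography vs Capnography) and the Conclusion also call the two tests equally reliable. The Discussion bases this on inspection of their separate confidence intervals. The same Discussion section says that an unmatched pair of results needs a third reliable method. For agreement, the Results report: "A kappa value of 0.749 with 95% confidence interval of" 0.567 to 0.931, standard error 0.093.

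**The concern.** Two binary tests can be merged in more than one way, and each way trades sensitivity against specificity. An accuracy figure for the pair means little until the rule is stated. Here the tally credits a tracheal tube if either test was right, but an oesophageal tube only if both were. That is a definite rule, but it is not named, and the Methods do not show that it was chosen before the data were seen. If another simple rule reverses the direction of the change, the conclusion that combining helps is a product of the choice.

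The equality claim is a separate fault of inference. Both tests were applied to the same 95 patients, so the comparison should be paired. Overlap of two separate intervals does not show equality, and no equivalence margin was set. Specificity rests on 11 tubes.

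Both statements are main messages of the report, so a reader may adopt the pair, or treat one test as a substitute for the other, on evidence that does not support it.

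**Working it through.** **Inputs.** Results, Table 8 (ultrasound): TP 82, FN 2, FP 1, TN 10. Table 9 (capnography): TP 81, FN 3, FP 0, TN 11. There were 84 tracheal and 11 oesophageal tubes.

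**Rebuilding the cross-table.** All 84 tracheal tubes were identified by at least one test, so the 2 ultrasound and 3 capnography false negatives are different patients, and both tests were right in 84 - 2 - 3 = 79. Capnography missed no oesophageal tube and ultrasound missed one.

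| Final position | Both right | Ultrasound only right | Capnography only right | Neither |
|---|---|---|---|---|
| Tracheal (84) | 79 | 3 | 2 | 0 |
| Oesophageal (11) | 10 | 0 | 1 | 0 |

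**Reproducing the stated figure.** Under 'tracheal if either says tracheal', TP = 84 and TN = 10, so accuracy = (84 + 10)/95 = 98.95%, which the report truncates to 98.94%. Under the opposite rule, 'oesophageal if either says oesophageal', TP = 79 and TN = 11, so accuracy = (79 + 11)/95 = 94.74%.

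**Each option with exact (Clopper-Pearson) 95% intervals.**

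| | Sensitivity | Specificity | Accuracy |
|---|---|---|---|
| Ultrasound alone | 82/84 | 10/11 | 92/95 = 96.84% (91.0 to 99.3) |
| Capnography alone | 81/84 | 11/11 | 92/95 = 96.84% (91.0 to 99.3) |
| Either says tracheal | 84/84 (95.7 to 100) | 10/11 = 90.9% (58.7 to 99.8) | 94/95 = 98.95% (94.3 to 99.97) |
| Either says oesophageal | 79/84 = 94.0% (86.7 to 98.0) | 11/11 (71.5 to 100) | 90/95 = 94.74% (88.1 to 98.3) |

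**Paired change in accuracy.** The difference is (gained - lost)/n, with Tango score intervals and exact McNemar p-values.

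- Either-tracheal v capnography: (3 - 1)/95 = +2.1 points (-3.0 to +8.0), p = 0.625.
- Either-tracheal v ultrasound: (2 - 0)/95 = +2.1 points (-1.9 to +7.4), p = 0.50.
- Either-oesophageal v capnography: (0 - 2)/95 = -2.1 points (-7.4 to +1.9), p = 0.50.

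**Ultrasound minus capnography.**

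- Accuracy: (3 - 3)/95 = 0 (-6.2 to +6.2).
- Sensitivity: (3 - 2)/84 = +1.2 points (-5.2 to +8.0).
- Specificity: (0 - 1)/11 = -9.1 points (-37.7 to +19.1).
- Exact McNemar p = 1.0 for all three.

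**Third-method reading.** The tests agree in 79 + 10 = 89 of 95 and are right in all 89 (95.9% to 100%). The other 3 + 2 + 1 = 6 of 95, or 6.3% (2.4 to 13.2), would go to the third method.

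**Kappa check.** The margins are ultrasound 83/12 and capnography 81/14. Chance agreement = (83 × 81 + 12 × 14)/95² = 6891/9025 = 0.7635. Observed agreement = 89/95 = 0.9368. Kappa = (0.9368 - 0.7635)/(1 - 0.7635) = 0.733, SE 0.103. With the margins fixed, agreement can change only in steps of two patients. The neighbouring values are 87/95 (0.644), 91/95 (0.822) and 93/95 (0.911). None gives 0.749.

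**The case against.** The arithmetic of 94/95 is right, and an attentive reader can recover both the rule and the missed oesophageal tube from the Results. Combined accuracy is not among the five specific objectives or the hypotheses. The Discussion's sentence is limited to this study, and as a point estimate 94 does exceed 92. The 90/95 rule is not proposed anywhere in the report. The third-method statement can be read as practice advice rather than a scoring rule. On equality, the Discussion grants that capnography seemed more specific, the wide specificity intervals are printed, and the Abstract's conclusion calls both tests reliable without calling them equal.

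Much of this stands. The rule is unnamed rather than hidden, and the sample statement is literally true. It does not cover the forward-looking claims in the Abstract and Conclusion, which generalise from two net patients. The second rule is needed as a check because it shows that the direction is not a property of the data alone. Printed intervals do not justify an equality claim that those same intervals contradict. The paired figures do depend on a cross-table that is inferred, not printed, and that conflicts with the stated kappa. That is a reason to check the source data.

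**Conclusion.** The concern holds. The 94/95 is reproducible but depends on the rule: accuracy changes by +2.1 points against either test under one simple rule and by -2.1 points under the other, and the intervals under both rules include no change. A gain from combining is therefore not shown. Under the rule actually used, specificity falls from capnography's 11/11 to 10/11.

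Equal reliability is not shown either. The non-significant paired tests are not evidence of equality, and the specificity interval allows a deficit for ultrasound of nearly 38 points.

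These results assume that Tables 8 and 9 and the joint statements in the Results are correct. At least one of those inputs or the reported kappa must be wrong, since 0.749 cannot arise from the margins of the two tables. No position is taken on which rule should be used in practice.

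**What to change.** 1. Print the cross-table of both tests by final tube position after checking it against source records. Correct whichever of Table 8, Table 9, the joint statements or the kappa is in error.
2. Name the combination rule, and say so if it was chosen after the data were seen. Report sensitivity, specificity and accuracy with exact intervals under both simple rules.
3. Report paired differences in accuracy, sensitivity and specificity between the tests, and in accuracy between the combination and each test, with intervals and exact McNemar p-values.
4. In the Abstract, Discussion and Conclusion, replace the claim of a gain and the claim of equality with a statement that no difference was shown and that the specificity comparison is too imprecise to support equality.
5. Give the concordant and discordant counts (89 and 6 on the present figures) and reconcile the combined figure with the Discussion's third-method statement.

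The cost is a small re-analysis of existing data, one check of source records and some rewording. The combined-accuracy message becomes less favourable.

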< 0.1	Large change in likelihood (or in other words high probability of any individual having a negative result on using the diagnostic test).
0.1 – 0.2	Moderate change in likelihood.
0.2 – 0.5	Small change in likelihood.
1	No change.

Data collection and management

The Pre-anaesthetic (PAC) form of the Department of Anaesthesiology, MMC, IOM; (Appendix A) was used to evaluate patients for inclusion into the study. All participants' data such as gender, age, ethnicity, diagnosis, BMI, weight, ASA status, medical comorbidities, airway examination was collected on data entry proforma sheet (Appendix C). The proforma sheet also recorded the baseline vitals and the vitals after induction of anaesthesia and after intubation. The results for ultrasonography and capnography, the respective time taken to obtain the results were recorded in the proforma sheet.

Data entry was done into Microsoft excel 2010. (Appendix E)

Statistical Analysis

Descriptive variables were expressed as mean \pm standard deviation, median, range, interquartile range, frequency, percentage and proportion. The calculations were done in Microsoft excel 2010.

The sensitivity, specificity, positive and negative predictive values, accuracy, along with their confidence intervals and likelihood ratios for positive and negative results were calculated by defining the respective mathematical functions into Microsoft excel 2010.

The mean and median times along with the interquartile range and standard deviations, taken for confirmation by capnography and ultrasonography were calculated using SPSS 23.0. Difference in time was calculated as method 1 (ultrasonography) minus method 2 (capnography) and reported as mean with 95% confidence interval; the results were compared using paired student t-test with p values at 95 % level of significance. The analysis was done using SPSS 23.0.

Kappa statistic was used to see agreement over and above that which would have occurred just by chance between these two methods. The kappa (κ) value was calculated using SPSS 23.0. It was interpreted based on the following criteria³⁸:

Table 4. Interpretation of kappa value.³⁸

Kappa value (κ)	Degree of agreement
0.81 - 1.00	Very good.
0.61 - 0.80	Good.
0.41 - 0.60	Moderate.
0.21 - 0.40	Fair.
<0.20	Poor.

[figure not shown]

Fig. 8. Study flow diagram.

(TP=True Positive, FP=False Positive, TN=True Negative, FN=False Negative)

RESULTS

Descriptive data

Demography

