Among the 95 subjects, the mean age was found out to be 44.24 years with standard deviation of ± 16.18 years, and the median age was 47 years. The youngest patient was of 16 years, and the eldest patient was 85 years old. Most patients were in the age group of 41 to 50 years.

Table 5. Demographic profile according to age.

Mean \pm SD (in yrs)	Median (in yrs)	Maximum (in yrs)	Minimum (in yrs)
44.24 \pm 16.18	47	85	16

(n=number, SD= Standard Deviation, yrs = years)

[figure not shown]

Fig. 9. Distribution of the subjects into different age groups.

Among the 95 subjects, there were 51 females (53.68%) and 44 males (46.32%) in this study.

[figure not shown]

Fig. 10. Sex-wise profile of patients in the study.

The majority of patients were Brahmins (40%), followed by Chhetris (22.10%), Newars (14.70%), Magars (7.36%), and others (15.84%); as shown in figure 11. Others include Rai (4), Bhaisnav (1), Chaudhary (1), Muslim communities (2), Lama (2), Gurung (1), Damai (1), Tamang (2), Thakuri (1) and Sherpa (1).

BMI

The mean body mass index (BMI) of the 95 patients was found to be 23.55 ± 3.58 (mean \pm standard deviation); the median BMI was 23.72 and the inter-quartile range [20.68 - 25.92], all values expressed in kg/m^2 . The summary is shown in table 3 and figure 12.

[figure not shown]

Fig. 11. Distribution of patients as per ethnicity in this study.

Table 6. Average body mass index (BMI) of patients.

	Mean \pm SD	Range	Median	IQR
BMI (kg/m^2)	23.55 \pm 3.58	16.33 - 33.88	23.72	[20.68 - 25.92]

(SD = Standard Deviation, Range = Maximum - minimum values; IQR = Interquartile range)

[figure not shown]

Fig. 12. Frequency of patients according to WHO classification of BMI.

ASA Physical Status

There were 46 ASA I patients and 49 ASA II patients in this study. The clinical conditions in patients with ASA II status are listed below in table 4. Table 4 does not account for the presence of multiple clinical conditions in the patients.

[figure not shown]

Fig. 13. ASA Physical status distribution of patients.

Table 7. Clinical conditions in ASA II patients.

	No. of patients	
	MCTVC	TUTH
Valvular heart disease	8	0
Coronary heart disease	14	1
Vascular disease	6	0
Hypertension	14	6
Diabetes Mellitus	4	1
Hypothyroidism	3	3
Hepatitis C positive	0	1
Central nervous system disease	0	8

Analytical Statistics and Data

Out of the total 95 intubations, there were 11 oesophageal intubations. The incidence of oesophageal intubation was 11.57% in this study.

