Ultrasonography

Ultrasound falsely detected one oesophageal intubation as tracheal, and two tracheal intubations as oesophageal.

Table 8. Distribution of positives and negatives for ultrasonography.

Position showed by Ultrasound	Endotracheal tube position confirmation		Total
	Trachea	Oesophagus	
Trachea (n)	TP = 82	FP = 1	83
Oesophagus (n)	FN = 2	TN = 10	12
Total	84	11	n = 95

(n=no. of patients, TP=True Positives, FP=False Positives, FN=False Negatives, TN=True Negatives)

The sensitivity, specificity, positive predictive value and negative predictive value (with their corresponding 95% confidence intervals in round brackets) were calculated to be 97.62% (91.66% - 99.71%), 90.91% (58.72% - 99.77%), 98.80% (92.67% - 99.81%) and 83.33% (55.66% - 95.22%) respectively. The positive likelihood ratio was 10.74, which suggested a large change in the likelihood of positive result. The negative likelihood ratio was 0.03 which also suggested a large change in the likelihood of negative result. The accuracy of ultrasonography in confirming endotracheal tube placement was 96.84% (92.92% - 100%).

[figure not shown]

Fig. 14. Distribution of positives and negatives for ultrasonography.

Capnography

There were three false negative results given by waveform capnography. There was no false positive result.

Table 9. Distribution of positives and negatives for capnography.

Position showed by waveform capnography	Endotracheal tube position confirmation		Total
	Trachea	Oesophagus	
Trachea (n)	TP = 81	FP = 0	81
Oesophagus (n)	FN = 3	TN = 11	14
Total	84	11	n=95

(n=no. of patients, TP=True Positives, FP=False Positives, FN=False Negatives, TN=True Negatives)

[figure not shown]

Fig. 15. Distribution of positives and negatives for capnography.

The sensitivity, specificity, positive predictive value and negative predictive value (with their corresponding 95% confidence intervals in round brackets) of capnography were calculated to be 96.43% (89.92% - 99.26%), 100% (71.51% - 100%), 100% (100% - 100%) and 78.57% (54.69% - 91.76%) respectively. The positive likelihood ratio was infinity. The negative likelihood ratio was 0.04 which suggested a large change in the likelihood of negative result. The accuracy of capnography in confirming endotracheal tube placement was 96.84% (92.92% - 100%).

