Hence these descriptive variables did not affect the outcome of the study. These variables reflect the demographic profile of the patients served at the academic centres of IOM in Maharajgunj and provide validity to the study. This data could help as reference for researchers who might carry out similar studies in the same centres in future.

Analytical Statistics

The incidence of oesophageal intubation was 11.57% in this study. Reported incidence of oesophageal intubations during elective intubation is less than 2%.^{12,39}

The incidence of oesophageal intubation increases up to 6 - 16 % during in-hospital emergency intubations.^{29,30,39,40}

Ultrasonography

In this study, the sensitivity, specificity, positive predictive value and negative predictive value (with their corresponding 95% confidence intervals) of ultrasonography were calculated to be 97.62% (91.66% - 99.71%), 90.91% (58.72% - 99.77%), 98.80% (92.67% - 99.81%) and 83.33% (55.66% - 95.22%) respectively.

The sensitivity of ultrasonography in this study is comparable to sensitivity reported in the meta-analyses done by Das et al²¹ and Chou et al⁶, which were 98% and 93% respectively. The specificity was 90.91% in this study, which is slightly lower compared to the above mentioned meta-analyses where specificity ranges from 97 to 98%.^{6,21} But the 95% confidence interval of specificity in this study extends from 58.72 to 99.77% which covers the reported specificity 97 to 98% in these meta-analyses. Thus the calculated pretest probabilities of ultrasonography in this study were not different from those reported in literature.

The PPV and NPV of ultrasonography calculated in this study were 98.8% and 83.33% respectively. The PPV of ultrasonography in this study is similar to that found by Adi et al³⁰, Chou et al²⁸, Chintamani et al³⁴ and Nasreen et al³³: the reported PPV ranges from 98 to 100% in these studies. The NPV of ultrasonography has been reported to be: 62.5% by Chintamani et al³⁴, 75% by Adi et al³⁰, 94% by Chou et al²⁸, and 96.77% by Nasreen et al³³. The 95% confidence interval of NPV of ultrasonography in this study was (55.66%- 95.22%), which is comparable to the NPV found by the above mentioned studies.

Ultrasonography had an accuracy of 96.84% in endotracheal tube confirmation in this study. Similar accuracy ranging from 97 to 98% had also been found by previous researchers.^{28,30,33}

There are various ways of using ultrasonography for endotracheal tube confirmation.

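### Objective 5 rests on one kappa that depends on the oesophageal rate, is compared across studies with different rates, and does not follow from the document's own tables

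*Combined protocol and SAP*

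**What the plan says.** Objective 5 is to interpret the degree of agreement between ultrasonography and capnography by kappa. The Statistical Analysis section gives the purpose: "Kappa statistic was used to see agreement over and above that which would have occurred just by chance between these two methods". Table 4 sets the bands: *fair* 0.21–0.40, *moderate* 0.41–0.60, *good* 0.61–0.80, *very good* 0.81–1.00, and *poor* below 0.20.

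The Results report kappa 0.749, 95% CI 0.567 to 0.931, SE 0.093, and conclude: "The kappa value therefore showed a good agreement between the result of these two methods". The Abstract and the Discussion repeat this. The Discussion (Ultrasonography vs Capnography) adds: "Other studies have shown a good or a very good agreement of these two methods by kappa statistics". It then lists four published values between 0.76 and 0.93.

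The Discussion (Analytical Statistics) puts this study's oesophageal rate at 11.57% and says: "Reported incidence of oesophageal intubations during elective intubation is less than 2" per cent.

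**The concern.** Both tests were scored against a confirmed final position, but agreement is summarised by one kappa over all 95 patients. Two reasonably accurate tests will agree because both follow the tube, and the size of kappa then depends on how many tubes were oesophageal. Three consequences follow.

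- The band label belongs to this sample's mix of tube positions. It cannot be set beside kappas from studies with other mixes.
- The question a reader would ask is how often the two methods disagree, and no rate is given. The Discussion makes this matter, because it says a third method is needed whenever the two results do not match.
- The printed kappa can be checked against Tables 8 and 9, and it does not match them.

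**Working it through.** **Inputs (Results).** "Out of the total 95 intubations, there were 11 oesophageal intubations", so 84 were tracheal. Ultrasound: "Ultrasound falsely detected one oesophageal intubation as tracheal, and two tracheal intubations as oesophageal" (Table 8: 82, 1, 2, 10). Capnography: "There were three false negative results given by waveform capnography", with no false positives (Table 9: 81, 0, 3, 11). On overlap: "The 84 tracheal intubations were correctly identified by both ultrasonography and capnography or either one of these methods". So no tracheal tube was misread by both. The same paragraph says both tests together identified 10 of the 11 oesophageal tubes.

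**Paired table.** These statements fix every cell:

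| True position | Both right | Capnography wrong only | Ultrasound wrong only | Both wrong |
|---|---|---|---|---|
| Trachea (84) | 79 | 3 | 2 | 0 |
| Oesophagus (11) | 10 | 0 | 1 | 0 |

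As verdicts: both tracheal 79, ultrasound tracheal with capnography oesophageal 3 + 1 = 4, the reverse 2, both oesophageal 10.

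**The printed figures.** The interval agrees with its own SE: 0.749 ± 1.96 × 0.093 = 0.567 to 0.931. The point estimate does not agree with the counts. With κ = (po − pe)/(1 − pe):

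- po = (79 + 10)/95 = 0.9368
- pe = (83 × 81 + 12 × 14)/95² = 6891/9025 = 0.7635
- κ = 0.1733/0.2365 = **0.733**

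Large-sample SE (Fleiss–Cohen–Everitt) = √(A + B − C)/[(1 − pe)√n], where r and q are the two tests' marginal proportions:

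- A = Σ p_ii[1 − (r_i + q_i)(1 − κ)]² = 0.3319
- B = (1 − κ)² Σ_{i≠j} p_ij(q_i + r_j)² = 0.0044
- C = [κ − pe(1 − κ)]² = 0.2798
- SE = **0.103**; 95% CI 0.733 ± 1.96 × 0.103, about 0.53 to 0.94

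The overlap statement is not the cause. With Tables 8 and 9 fixed, 0, 1 or 2 shared false negatives give κ = 0.733, 0.822 or 0.911. A search of nearby tables with n = 95 finds 0.749 only for cells such as 78/4/2/11 or 78/3/3/11. Their margins contradict Table 8 or both tables, and their SE is about 0.097, not 0.093.

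**Agreement within true position.**

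- Trachea: po = 79/84 = 0.9405; pe = (82 × 81 + 2 × 3)/84² = 0.9422; κ = −0.03.
- Oesophagus: po = pe = 10/11; κ = 0. This is forced, because capnography gave the same verdict in all 11.

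Two tests with these error rates and wholly unrelated errors would give an overall κ of 0.739 at this mix, against 0.733 observed.

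**Dependence on the oesophageal rate p.** Hold the observed error rates fixed, with no shared errors:

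- both oesophageal: p × 10/11
- ultrasound oesophageal: (1 − p) × 2/84 + p × 10/11
- capnography oesophageal: (1 − p) × 3/84 + p
- discordance: (1 − p) × 5/84 + p × 1/11

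| p | Source in the document | κ | Table 4 band | Discordance |
|---|---|---|---|---|
| 2% | upper bound cited for elective intubation | 0.35 | fair | 6.0% |
| 5.6% | cited study with κ = 0.85 | 0.59 | moderate | 6.1% |
| 11.6% | this study | 0.73 | good | 6.3% |
| 16% | upper end cited for in-hospital emergencies | 0.78 | good | 6.5% |

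Below 2% kappa keeps falling: 0.20 at 1% and 0.10 at 0.5%.

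**Precision of the 2% projection.** Setting both false-negative rates at the limits of the reported sensitivity intervals, with independent errors, gives about 0.15 to 0.75. One shared false negative would give 0.60.

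**Discordance in this sample.** (4 + 2)/95 = 6.3%; Clopper–Pearson 95% CI 2.4 to 13.2.

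**The case against.** Much can be said for the analysis as reported. Kappa was the stated method, chance is meant in Cohen's marginal sense, and *good* is the correct band at either 0.749 or 0.733. Two valid tests that agree because both follow the tube do agree. The interval is printed wherever the value appears, no sentence says the value holds at a 2% rate, and the Conclusion and Recommendations do not mention kappa. All of this stands.

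Four stronger readings are tempting, and the documents do not support them.

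- *The tests agree no better than chance once position is known.* The tracheal value rests on five errors. Under independence only 84 × (2/84) × (3/84) = 0.07 shared errors are expected, with a 93% chance of none. One shared error would have moved tracheal kappa to 0.38. The data show no evidence of agreement beyond position but cannot exclude it.
- *Kappa adds nothing to the two accuracies.* It does add something: with both accuracies fixed, it is 0.733, 0.822 or 0.911 according to how many errors are shared.
- *Agreement in elective practice would be fair.* The projection assumes that error rates carry over, and its range is wide. Since the cited rate is below 2%, *fair* is also the favourable end.
- *The absence of shared errors was withheld.* The Results imply it; they do not state it outright.

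**Conclusion.** The point holds as one of interpretation and reporting, with one numerical inconsistency. The label *good* is right for this sample but describes a sample with 11.6% oesophageal tubes. At fixed error rates kappa would range from about 0.35 to 0.78 between 2% and 16%, while discordance stays near 6%. The comparison with kappas of 0.93 and 0.85, from studies at 15.2% and 5.6%, is therefore not like for like. At 5.6% this study's error rates would give about 0.59. Even at face value the interval spans three bands, *moderate* to *very good*.

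The printed 0.749 (SE 0.093) does not follow from the document's own counts, which give 0.733 (SE 0.103). The band does not change.

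The recalculated kappa relies on Tables 8 and 9 and the two overlap sentences being correct. The projections further assume that error rates do not change with the setting and rest on six errors, so they show the direction and rough size of the dependence and are not estimates for other settings.

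**What to change.** In the Results, under Objective 5:

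- Report the paired table by true position shown above.
- Give the discordance rate, 6/95 = 6.3% (95% CI 2.4 to 13.2), and state in words that no patient was misclassified by both tests.
- Reconcile the printed kappa, SE and interval with Tables 8 and 9. If the tables are right, these become 0.733, 0.103 and about 0.53 to 0.94. If they are not, correct the tables.
- Keep kappa with its interval as a descriptive figure, and say that it belongs to a sample with 11.6% oesophageal tubes and that the interval covers *moderate* to *very good*.

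Carry the same wording into the Abstract and Discussion. In the Discussion, remove the comparison with published kappas, or qualify it by giving each study's oesophageal rate where known and noting that kappa depends on it.

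All of this uses existing data: one small table, one rate and a few reworded sentences. The cost is a less favourable headline and slightly more reporting.
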